7.1.2.4 End of treatment (EOT) visit - amended

Within the trial close-out window prior to the end of the study (efficacy cut-off date), all patients must return to the clinic within 6 weeks in order to make a final assessment. In addition, for patients that permanently discontinued study medication and when further follow-up will no longer be done by site visits and rather by phone or third party contact, the patient will be encouraged to come for the EOT visit as soon as possible after discontinuation of study medication. For these patients a final vital status and outcome events will be collected during the trial close-out window. At this EOT visit, study procedures will include the collection of efficacy and safety outcome data, (S)AEs, vital signs, ConMeds, EQ-5D,

³¹ Sentence was added with global Protocol Amendment 5 to allow flexibility for patients after a stroke.

³² Global Protocol Amendment 5 added “or study outcome event” to this sentence for clarification.

³³ The DSS test was removed with global Protocol Amendment 5 because implementation is not feasible due to a missing license.

³⁴ The 3-month time point was expanded to 3-6 months with global Protocol Amendment 5 to allow flexibility and avoid additional visits.

MoCA, and SAGE questionnaires, and modified Rankin score. In addition, the study staff will collect the patient's empty and unused study medication bottles to allow final drug accountability and compliance checks.³⁵

Study medication will be stopped at this visit, and it will be left to the discretion of the investigator to initiate any antiplatelet or anticoagulation therapy during the transition of care to the patient's personal physicians.

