7.6.1.4 Modified Rankin Score - amended

In addition to the regular assessments at screening, 1 year, and EOT, the Modified Rankin Score will be assessed by the investigator at 7 days or at discharge, if this occurs before 7 days, and again at 3-6 months⁴¹ after a recurrent stroke. The scale spans 0-6, perfect health without symptoms to death.

- 0 - No symptoms.
- 1 - No significant disability. Able to carry out all usual activities, despite some symptoms.
- 2 - Slight disability. Able to look after own affairs without assistance, but unable to carry out all previous activities.
- 3 - Moderate disability. Requires some help, but able to walk unassisted.
- 4 - Moderately severe disability. Unable to attend to own bodily needs without assistance, and unable to walk unassisted.
- 5 - Severe disability. Requires constant nursing care and attention, bedridden, incontinent.
- 6 - Dead.

8. Statistical methods and determination of sample size

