## 4.5 Data Rules

### 4.5.1 Analysis Dates - amended

For the study the following date and time window are of relevance for the analysis:

- Efficacy cut-off date:  
The efficacy cut-off date is the 5th of October 2017, the date the early stopping of the trial was officially announced.
- Trial close-out window:  
The Trial close-out window is the time period when all subjects are to return to the clinic for an End of treatment Visit.

For each subject, the following individual dates are of relevance for analysis:

- Randomization date:  
The date of randomization to antithrombotic study treatment of the subject.
- End of treatment (EOT) Visit date:  
This is the date of the EOT Visit for the individual subject.  
After the announcement of the end of the study, all subjects are to return to the clinic for their EOT Visit within the pre-specified window (Trial close-out window).  
If subjects do not have an EOT visit, the date will be missing.
- Date of the last contact prior or equal to efficacy cut-off:  
This date is defined as the date of the last trial contact or the efficacy cut-off date, whatever comes first.
- Date of the last trial contact:  
The date of the last documented contact with the subject or a third party (including data on subject survival status).  
For subjects who die after randomization the date of the last contact is set to the death date.
- Date of first double-blind dose of antithrombotic study treatment:  
The date of the first dose of rivaroxaban / aspirin study medication.
- Date of last double-blind dose of antithrombotic study treatment:  
The date of the last dose of rivaroxaban / aspirin study medication.  
For a subject with permanent discontinuation of any study medication, the corresponding last dose date(s) will be obtained from the CRF "Study Medication Discontinuation/Restart Report". If study medication was continued until the EOT visit, the date of the last dose of the corresponding study medication will be as reported on the EOT visit CRF.  
If missing or incomplete, the date of last double-blind dose of antithrombotic study

treatment is set to the latest logically possible date of antithrombotic study medication administration on or before the earliest of the subject's following dates, the date of last trial contact, the date of death, or the efficacy cut-off date, and no earlier than the randomization date.

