#### **6.5 Other procedures and variables**

The analysis of other variables will be by treatment group and overall and based on ITT.

Other variables are:

- Healthcare Resource Use
  - hospitalizations (total days length of stay, intensive care unit/cardiac care unit days, ward type); emergency room visits; unscheduled outpatient physician consultations; or visits related to bleeding, surgeries, other selected procedures (inpatient and outpatient); and post-stroke care (status of care, home health or rehabilitation center or long term care). Days off-work.
- European Quality of Life-5 Dimensions (EQ-5D)
  - EQ-5D is a standardized measure of health status developed by the EuroQol Group in order to provide a simple, generic measure of health for clinical and economic appraisal. Assessments will be done using both a descriptive system and the subject's self-rated health on a visual analogue scale where the endpoints are labeled 'Best imaginable health state' and 'Worst imaginable health state'.  
The following variables are of interest:
    - EQ-5D single dimensions
    - EQ-5D Visual Analogue Scale (VAS) values
    - EQ-5D index score
  - EQ-5D will be analyzed separate from section 14 of CSR.
- Montreal Cognitive Assessment (MoCA)
  - The Montreal Cognitive Assessment (MoCA) test assesses several cognitive domains: attention and concentration, executive functions, memory, language, visuoconstructional skills, conceptual thinking, calculations, and orientation. For each task correctly completed, one point is assigned. All subscores are summed up and adjusted for individuals with  $\leq 12$  years education to derive a total score ranging between 0 (for a totally cognitive impaired subject) and a maximum of 30 points (cognitively healthy participant).
- Standard Assessment of Global-Activities in the Elderly (SAGE)
  - The SAGE questionnaire comprises 15 items, each describing an activity for which the respondent has to indicate how much difficulty the subject has encountered in performing this activity in the past month. Regarding scoring for an item, 0 points are assigned if the participants endorse the "None/never performed" response, 1 point to the "Mild" response, 2 points to the "Moderate" response, and 3 points to the "Severe" response. One additional point will be assigned when in response to question 11, 12, and 15 the

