respondent declares the need for help from another person or a tool to walk, jump the stairs or to bath. The total score will range from 0, describing a very independent participant over a broad spectrum of activities, to 48, describing a very dependent subject.

- Modified Rankin Score
  - The modified Rankin Score runs from 0-6, running from perfect health without symptoms to death.
  - The score will be analyzed by frequency tables and bar charts comparing baseline to EOT. Wilcoxon rank-sum test will be used to give exploratory p-values comparing treatment groups.

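### SAP 6.5 has no rule for scoring deaths in the end-of-treatment Rankin comparison, so on recorded scores most patients who died would drop out

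*SAP*

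**What the plan says.** SAP 6.5 defines the scale: "The modified Rankin Score runs from 0-6, running from perfect health without symptoms to death". Protocol 7.6.1.4 agrees ("The scale spans 0-6, perfect health without symptoms to death") and lists 6 as the category for a patient who is dead.

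The planned analysis is short. "The score will be analyzed by frequency tables and bar charts comparing baseline to EOT", and a "Wilcoxon rank-sum test will be used to give exploratory p-values comparing treatment groups". The population is set at the head of the section: "The analysis of other variables will be by treatment group and overall and based on ITT". SAP 5.1.1 defines that set as everyone randomized.

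On timing, Protocol 7.6.1.4 states: "In addition to the regular assessments at screening, 1 year, and EOT, the Modified Rankin Score will be assessed by the investigator at 7 days" after a recurrent stroke (or at an earlier discharge), and again at 3-6 months. The EOT assessment is a clinic visit. Protocol 7.1.2.4 says that in the close-out window "all patients must return to the clinic within 6 weeks in order to make a final assessment". The same section, with footnote a of the table of procedures, provides an earlier EOT visit for a patient who has permanently stopped study medication and will have no more site visits. For such a patient, only vital status and outcome events are gathered at close-out.

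On an absent visit, SAP 4.5.1 says: "If subjects do not have an EOT visit, the date will be missing". That defines a date, not a score. SAP 4.3 covers listing missing data as recorded and estimating event dates. SAP 4.5.5 covers repeated measurements. None of these assigns a Rankin score to a patient who died.

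**The concern.** The scale has a category for death, but the analysis reads its values from a visit that a dead patient cannot attend. Exclusion criterion 1 in Protocol 5.1.2 keeps out patients with a score of 4 or more at screening, so category 6 can be filled only by deaths during the study. If nothing carries those deaths into the EOT score, an analysis labelled ITT omits its worst outcomes.

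Where mortality differs by arm, the patients left to be scored differ too. The arm with more deaths could then look no worse, or even better, on function. Two programmers following the same text could report different p-values.

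**Working it through.** **Step 1. What happens to each kind of patient if only recorded EOT scores are used**

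- Died with no EOT visit: no EOT score, so the patient is missing from the test.
- Died after an early EOT visit: the recorded score stands, so the patient enters with a value from before death.
- Died between the efficacy cut-off and the close-out visit: no EOT score unless there was an early EOT visit. SAP 4.5.1 sets the cut-off at 5 October 2017, the announcement date, and has patients return for EOT after the announcement. The ITT data scope in SAP 4.5.2 ends at the cut-off, so a death rule tied to that scope would miss these patients.
- Alive with no EOT visit: missing.

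The ITT label does not settle the matter. The same sentence in SAP 6.5 also governs MoCA and SAGE, which have no rule for deaths either.

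**Step 2. How many patients**

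The documents give no sample size, power or expected result for this comparison, so there is no stated figure to reproduce. Inputs:

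- 3500 patients per arm, 7000 in total (SAP 4.6)
- 3% deaths per year (SAP 4.6)
- 2 years of recruitment and 3 years in total, so 1 to 3 years of follow-up (SAP 4.6); mean treatment duration of about 2 years (Protocol synopsis)

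At a flat 2 years: 3500 × (1 − 0.97²) = 3500 × 0.0591 = 207 per arm, or 5.9%.

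With follow-up uniform on 1 to 3 years and constant hazard h, the mean share dead is 1 − (e^(−h) − e^(−3h)) / (2h):

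- h = 0.03: 1 − (0.97045 − 0.91393)/0.06 = 0.058, or 407 of 7000 (about 203 per arm)
- h = −ln 0.97 = 0.03046: 1 − (0.97000 − 0.91267)/0.06092 = 0.059, or 413 of 7000 (about 206 per arm)

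The trial stopped early and the documents do not give the follow-up actually reached. If it averaged only 1 year, the share is 3.0%, or 105 per arm.

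**Step 3. Whether the choice can move the test**

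This is an illustration on assumed inputs, none of them from the documents. Survivors are distributed 25/33/22/14/5/1% over scores 0 to 5, identically in both arms, and only mortality differs. The test is taken as a comparison of EOT scores with n = 3500 per arm.

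With deaths scored 6, the probability that a random patient in one arm scores worse than one in the other (ties counted half) differs from 0.5 by half the difference in mortality. Its standard error is √[(1 − Σm³)/12 × 2/n], where m is the pooled share in each category.

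- Mortality 6% and 8%: difference 0.010; Σm³ = 0.0527; standard error = √(0.9473/12 × 2/3500) = 0.00672; |Z| = 1.49
- Mortality 6% and 5%: difference 0.005; Σm³ = 0.0551; standard error = 0.00671; |Z| = 0.75

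With deaths left out, expected Z is 0 in both cases, because survivors were assumed identical. Neither value reaches 1.96, but the two readings give different p-values.

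**The case against.** A reader might infer that the SAP restricts the Wilcoxon test to survivors. It does not say so. A 0-6 scale ending in death, an ITT basis and recorded death dates are all compatible with scoring deaths as 6. What stands is that no rule says so, and SAP 4.3 lists missing data as recorded without replacing scores. The plain run of the text therefore loses most deaths.

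A reader might also infer that no patient who died has an EOT score. The early EOT visit shows otherwise. This lowers the number who drop out, but it adds patients who enter with a score that death has overtaken.

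The rule may exist elsewhere. SAP section 1 places programming instructions in a separate output specification, which is not among the documents. That cannot be excluded, but the same section says that the SAP itself contains the key derived variables.

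The strongest objection concerns consequence, and it stands. The p-values are labelled exploratory, and the EOT Rankin score is not among the ordered secondary outcomes in SAP 6.2.2. All-cause mortality is the second of those outcomes, and CV death is also analysed. Fatal bleeding counts in major and life-threatening bleeding (SAP 6.4.2 and 6.4.3), and SAP 6.6 adds mortality as a net-benefit measure. A difference in deaths would be visible beside any Rankin table, so the documents do not support a fear that it would be hidden.

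**Conclusion.** The point holds as a missing derivation rule in an exploratory analysis. The plan uses a scale whose worst category is death, takes the score at a clinic visit, and does not connect the two. On recorded scores, most deaths drop out and some enter with a pre-death value.

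Up to about 6% of patients, roughly 200 per arm, are affected. This assumes the plan's 3% yearly mortality and about 2 years of mean follow-up. It is an upper bound: it counts every expected death, follow-up may have been shorter after the early stop, and a specification not seen here may already score some or all deaths as 6. The effect on the p-value depends on a mortality difference between arms, for which the plan gives no figure. No confirmatory conclusion depends on it.

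**What to change.** In SAP 6.5, assign a Rankin score of 6 at EOT to every randomized patient who died before the close-out EOT assessment. State that this includes deaths after an early EOT visit, where 6 replaces the recorded score, and deaths between the efficacy cut-off and the EOT visit. For a patient with no close-out visit, the end of the trial close-out window can serve as the limit.

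Run the Wilcoxon test and the frequency tables on this set, and show the table of recorded EOT scores as supportive. Do not carry a last score forward for survivors: it might be a 1-year score or one taken 7 days after a stroke, and some patients would have none. Report the number of survivors without an EOT score by arm instead.

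The cost is a few lines of derivation and one extra table. No new data are needed, because SAP 4.2 already requires survival status for all subjects at the end of the study.

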## 6.6 Net clinical Benefit

The benefit-risk of rivaroxaban vs aspirin will be evaluated based on the excess number of events between treatments for events intended to be prevented (benefits) and events that may be caused (risks). Excess number of events is defined as the difference in event rate times a hypothetical population size (eg, 10,000 patients). To have a comprehensive benefit-risk evaluation, several comparisons will be considered.

The first measure of net clinical benefit in this study is the primary efficacy outcome. Although named efficacy outcome it includes not only thrombotic events, but also hemorrhagic events (hemorrhagic stroke).

The second measure of net clinical benefit is all-cause mortality.

The third measure of net clinical benefit is the composite of stroke, MI, CV death, fatal bleeding or bleeding into a critical organ.

As an overall valid measure of net clinical benefit is hard to be defined, a variety of measures will be presented side by side to allow weighting positive effects and harms. For the efficacy these will include the thrombotic events of the primary and secondary efficacy endpoints. For the safety side these will include the hemorrhagic events of the efficacy endpoint, ISTH major bleeding, life-threatening bleeding, and intracranial hemorrhage.

Other measures may be added as they may help to assess the net clinical benefit.

## 7. Document history and changes in the planned statistical analysis

- Draft SAP dated 30 Sep 2014
- Second SAP draft for team review dated 10 Nov 2014
- Proposed final SAP for team review dated 14 Jan 2015
- Approval of the SAP dated 2 Mar 2015
- Amendment 1 of the SAP dated 19 May 2017

- Amendment 2 of the SAP dated 20 Dec 2017

## 7.1 Overview Changes to SAP – Amendment 1

Editorial, administrative, and typographical corrections were made that do not affect the overall integrated SAP. These changes are not described in this section.

The following changes are introduced in SAP Version 2.0.

### **Modification 1:** Additional interim analysis at 50% of events

Rationale: Changes reflect those in global Clinical Study Protocol amendment 2.0 to be in line with the plan for interim analyses of the IDMC Charter as requested by the IDMC.

Section affected: 4.4 Interim Analyses and Data Monitoring

### **Modification 2:** Subgroup definition for age added and for region and cardiac rhythm monitoring clarified

Rationale: Additional age group (<60; >=60 years) is reflecting the strata used for randomization. Region definition was added. The derivation of the length of cardiac rhythm monitoring was clarified.

Section affected:

- 6.1.2 Demographics
- 6.2.3 Subgroup variables
- Appendix B: Region definition

### **Modification 3:** Details added/corrected for descriptive statistics

Rationale: “Index stroke” was changed to “qualifying stroke” to reflect the terminology of the CRF. Wording “last contact prior to efficacy cut-off” was clarified to “last contact prior or equal to efficacy cut-off”. The analysis of medical history and concomitant medication was adapted to the CRF design (pre-defined terms). The definition of the efficacy variable component CV death was clarified to include death with undetermined/unknown cause. The SAS code provided for carrying out the stratified log-rank test has been updated to reflect the FDA preferred implementation, with the difference being how tied event times are handled. Term corrected from ”AE” to “SAE” in adverse event section. Analysis method for modified Rankin score added. And the DSS was deleted following the protocol amendment.

Section affected:

- 4.5.4 Determination of baseline values (new)
- 4.5.5 Handling of repeated measurements (new)
- 6.1.3 Medical history
- 6.1.5 Prior and Concomitant Medications

- 6.2.2 Secondary efficacy variables
- 6.2.4 Analysis of the primary efficacy variable
- 6.4.1 Adverse events
- 6.5 Other procedures and variables

**Modification 4:** Added third measure of net clinical benefit

Rationale: The rationale is the specification of a measure for net clinical benefit that captures the major adverse events (stroke, MI, CV death) and important safety outcomes (fatal bleeding or bleeding into a critical organ). These are all likely modified by the study treatment.

Section affected:

- 6.6 Net clinical Benefit

## 7.2 Overview Changes to SAP – Amendment 2

**Modification 5:** Exclusion of bleeding events from AE reporting

Rationale: In Japan bleeding events are additionally reported as AEs. To avoid double counting, bleeding events will be excluded from the AE analysis using the SMQ Haemorrhage terms (excl laboratory terms). Bleeding events will be analyzed separately.

Section affected:

- 6.4.1 Adverse events - amended

**Modification 6:** Setting the efficacy cut-off date to October 5th 2017

Rationale: On October 5th 2017 the early stopping of the study was announced after the recommendation by the IDMC. The definitions of the efficacy cut-off date, the trial close-out window and the date of last contact prior or equal to the efficacy cut-off date have been adapted. This adaptation was made in the description of the ITT data scope and the ITT censoring rules accordingly. Within the sensitivity analyses section for the primary efficacy outcome the obsolete tipping point analysis has been deleted and an analysis including efficacy outcome events up to the date of the last trial contact has been added.

Sections affected:

- 1. Introduction
- 4.5.1 Analysis Dates
- 4.5.2 Data Scopes

- 4.5.3 Censoring rules for time-to-event variables
- 6.2.7 Sensitivity analyses

**Modification 7:** Detailed description added for the calculation of treatment compliance.

Section affected:

- 6.1.6 Extent of Exposure and Compliance

Appendix A: Patient follow-up

- 1) For all patients except cases of death it is expected that they stay in the study until the end of study (efficacy cut-off date) is announced. This is also true for patients that experience an outcome event!
- 2) EOT visit takes place during Trial close-out window unless patient not willing to come for regular visits

**Appendix B: Region definition - amended**

For subgroup analyses according to region, countries will be assigned to regions as shown in [Table 1](#). below. If additional countries participate in the trial, their assignment to a region will be described in an amendment to the SAP before unblinding.

**Table 1. Classification of countries to regions**

Region	Countries
North America	Canada, USA
South America	Argentina, Brazil, Chile, Mexico
Western Europe (plus Australia, Israel, and South Afrika)	Australia, Austria, Belgium, Denmark, Finland, France, Germany, Greece, Ireland, Israel, Italy, Portugal, South Africa, Spain, Sweden, Switzerland, United Kingdom
Eastern Europe	Czech Republic, Hungary, Poland, Russian federation, Turkey
Asia Pacific	China, Japan, South Korea
